## PRÉCIS

## **Background:**

• Patients with the familial cancer syndrome von Hippel-Lindau (VHL) demonstrate manifestations in a variety of organs among them the pancreas. Pancreatic manifestations can range from benign cysts and micro cystic adenomas to neuroendocrine tumors of the pancreas which are capable of regional and distant spread. These neuroendocrine tumors can result in life-threatening complications.

• This protocol is designed to identify VHL patients with pancreatic manifestations and to follow these patients with serial imaging studies and germ line and tissue genetic analysis.

## **Objectives:**

- To identify patients with VHL having pancreatic lesions defined by simple cysts, microcystic adenomas, neuroendocrine tumors and other solid lesions of the pancreas.
- To follow patients with VHL and pancreatic manifestations by serial examination with non-invasive imaging studies
- For patients with solid lesions of the pancreas, to determine the rate of growth and to correlate the growth rate with clinical measures of disease progression
- To validate non-invasive imaging methods for differentiating benign solid lesions from lesions with malignant potential
- To characterize the time from initial presentation with pancreatic tumors to the time that surgery is recommended.

#### **Eligibility:**

- Patients  $\geq 12$  years of age who have been diagnosed with VHL
- Patients/parent must be able to sign an informed consent and be willing to return to NIH for follow-up.

#### Design:

- Demographic data will be collected from the medical record and patient interview for each patient participant. Data will be securely stored in a computerized database.
- Patients will be evaluated by the Urologic Oncology Branch personnel as indicated to rule out or manage other manifestations of VHL. Imaging studies of regions other than the chest and abdomen will be dictated by best clinical practice for the workup and management of VHL manifestations as has been previously published.
- All patients enrolled on this study will be offered genetic counseling by a trained genetic counselor.

Version Date: 08/23/2017

• After their initial on-study evaluation, patients who are not found to have solid lesions of the pancreas but rather have only cystic disease of the pancreas, will be re-screened every two years with non-invasive imaging studies

- Surgical resection of solid lesions of the pancreas will be recommended based on previously published criteria.
- Based on our analysis of likelihood of tumor growth or risk of metastasis, data will be analyzed every two years and appropriate revisions will be made to the surgical management guidelines, if indicated by data analysis.
- Projected accrual will be 25 patients per year for a total of 15 years. Thus, we anticipate accruing 600 patients on this protocol.

*Abbreviated Title:* Pancreatic lesions in VHL *Version Date:* 08/23/2017

#### 1 INTRODUCTION

#### 1.1 STUDY OBJECTIVES

## 1.1.1 Primary Objectives

- To identify patients with VHL having pancreatic lesions defined by simple cysts, microcystic adenomas, neuroendocrine tumors and other solid lesions of the pancreas.
- To follow patients with VHL and pancreatic manifestations by serial examination with non-invasive imaging studies consisting of CT scan, MRI scan, PET-CT scan, and as clinically indicated, abdominal ultrasound.
- To determine if FDG and FDOPA PET scans can detect early tumor metastasis, and predict which patients will have tumor progression and require an operation based on uptake status. Note: this objective has been met for FDOPA PET imaging. See section 8.
- For patients with solid lesions of the pancreas, to determine the rate of growth and to correlate the growth rate with clinical measures of disease progression such as symptoms.
- To validate non-invasive imaging methods for differentiating benign solid lesions, such as microcystic adenomas, from lesions with malignant potential, namely pancreatic neuroendocrine tumors.
- To characterize the time from initial presentation with pancreatic tumors to the time that surgery is recommended.

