## 3.1.3 Non-invasive imaging

- CT scan with contrast of the chest, abdomen, and pelvis
- MRI of the abdomen with special attention to the pancreas as indicated
- Abdominal ultrasound exam as indicated by the CT and MRI scans to further evaluate cystic lesions.
- FDG PET scans for pancreatic lesions that are solid on CT scan or MRI.

**NOTE:** Due to the amount of radiation exposure, PET imaging will NOT be performed on children under the age of 18 or pregnant or nursing women.

Bi-dimensional tumor measurements will be performed on contrast CT scans to evaluate rate of tumor growth and tumor doubling, on scans obtained at baseline and at each follow up visit.

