#### 3.2 FOLLOW-UP EXAMINATIONS

Scheduling of follow up evaluations will be coordinated with UOB and/or NOB as appropriate.

- 3.2.1 Patients who are found to have only cystic disease of the pancreas or who have had surgery and who no longer have PNETs may undergo the following evaluations yearly for 2 years and then every two years if no evidence of malignant disease:
  - MRI, US and CT scan of the abdomen with contrast as indicated
  - metanephrines and normetanephrines
  - Chromogranin A
  - Research blood may be collected during follow up (once a year for patients with solid lesions or every two years for patients with cystic lesion) for correlative studies (validation of biomarkers of disease identified from tumor tissue analysis).

**Note:** Patients may be evaluated on a more frequent basis if they develop symptoms consistent with their cystic disease or have evidence of malignant disease recurrence.

- 3.2.2 Patients with solid lesions of the pancreas that are suspicious for PNETs that have not yet reached size criteria where surgery will be recommended (see below) may undergo the following evaluations yearly:
  - CT scans of the abdomen and pelvis with contrast, as well as an MRI scan of the abdomen.
  - FDG PET and PET-MRI scans –patients with solid lesions will undergo PET imaging as follows: Patients who are enrolled on Amendment F will undergo PET imaging at baseline and at one year. Patients who were enrolled prior to Amendment F will undergo PET imaging at their next imaging time point and again in one year.
  - Metanephrines and normetanephrines
  - Chromogranin A
  - Research blood may be collected during follow up (once a year for patients with solid lesions or every two years for patients with cystic lesion) for correlative studies (validation of biomarkers of disease identified from tumor tissue analysis).

**Note:** Due to the amount of radiation exposure, PET imaging will NOT be performed on children under the age of 18 or pregnant or nursing women.

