#### 8 STATISTICAL CONSIDERATIONS

We will estimate the distribution of time from initial presentation with pancreatic tumors to the time that surgery is recommended with a Kaplan-Meier Curve. An age-adjusted comparison between this distribution by mutational status (missense vs non-missense mutation, for example) will be done with a proportional hazards model using the method of Wei, et al. (Wei, L.J., Lin, D.Y., and Weissfeld, L., Regression analysis of multivariate incomplete failure time data by modeling marginal distributions. Journal of the American Statistical Association, 84, 1065-1073, 1989) to account for the lack of independence due to familial correlation.

We will estimate the growth rate in solid pancreatic tumors using linear and nonlinear mixed models (Davidian, M. and Giltinan, D.M., Nonlinear Models for Repeated Measurement Data, Chapman and Hall, New York, 1996). These models will allow for the various sources of correlation due to multiple members in the same family and multiple tumors on the same patient. We will compare the growth rate by mutational status as well as by clinical and imaging characteristics by including these factors as covariates in the mixed models. The choice of the form of the linear or non-linear model will depend on the observed data. We will use a linear mixed model on log-transformed volume data if the volume data appears approximately linear on the log-scale. Otherwise, we will investigate alternative models such as the Gompertz model for tumor growth.

The uptake levels of FDG on PET imaging will be compared between patients who require operative intervention and those who do not in order to determine the predictive value of PET imaging in this patient population. Power is based on comparing mean uptake between these two groups of patients. Based on the VHL patient characteristics collected at the Urologic Oncology Branch, NCI, assuming approximately 17% (52 patients) of the targeted 300 VHL patients screened in this study will have solid pancreatic lesion and 50% (26 patients) of them will require operation, we would have 94% power to detect 1 standard deviation difference in the mean uptake between the two groups. The comparison is based on the two-sample t-test at the 5% significance level.

Version Date: 08/23/2017

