Based on our analysis of likelihood of tumor growth or risk of metastasis, data will be analyzed every two years and appropriate revisions will be made to the surgical management guidelines, if indicated by data analysis.

As of February 1, 2011, 40 patients have been enrolled who have undergone all four imaging modalities (CT scan, MRI, 18F-DOPA, 18F-FDG). Only 11 of the 98 lesions (11%) were positive on 18F-DOPA as compared to CT scan. Based on this interim analysis, 18F-DOPA is not likely to be useful for detecting pancreatic neuroendocrine tumors in patients with VHL and as of amendment H this mode of imaging is no longer included in protocol evaluations.

As of April 15, 2014, 129 of 276 patients screened in the study had solid lesions. Of these 129 patients, 24 required operative intervention. FDG-PET detected metastatic disease in 3 patients which were not detected by CT, and found non-neoplastic disease in 4 patients. Hence, FDG-PET was able to find 29% of the surgical patients who either had metastasis not detected by CT or had non-neoplastic disease in which operation could be avoided. Using the method of Agresti-Coull (1998), the corresponding 90% confidence interval is (16.5%, 46%) with width 29.5%. Assume that the true proportion of diagnosis of metastatic as well as non-neoplastic disease by FDG-PET which is not detected by CT is 30%. To reduce the width of the 90% expected confidence interval to 20%, a total of 52 surgical patients are required. Correspondingly, approximately a total of 600 VHL patients need to be screened.

Power calculation for the comparison of tumor growth rates between two groups is based on comparing linear growth on the log-scale. Assuming that approximately 9% (54 patients) of screened VHL patients will present or develop pancreatic tumors which require operation over follow-up, we would have 95% power to detect a 1 standard deviation change in the growth rate between two groups of equal numbers (27 in each group) with a two-sided test the 0.05 significance level. This calculation is based on comparing individually estimated slopes (using multiple follow-up measurements on each subject) with a two-sample t-test. This calculation is only an approximation since power may be slightly reduced due to correlation across multiple individuals in the same family and may be increased due to multiple tumors followed on each patient.

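### The FDG comparison in Section 8 is read as predictive, but nothing keeps out patients who already met a surgery criterion at the PET

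*Combined protocol and SAP*

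**What the plan says.** The objective in Section 1.1.1 looks forward: FDG PET should "predict which patients will have tumor progression and require an operation based on uptake status". Section 8 carries it out as follows: "The uptake levels of FDG on PET imaging will be compared between patients who require operative intervention and those who do not", and gives the purpose as "in order to determine the predictive value of PET imaging in this patient population". The test is a two-sample t-test at the 5% level, with 94% power for a 1 SD difference between 26 operated and 26 non-operated patients.

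Four other places determine who enters that comparison.

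- Section 3.1.3 lists, among the on-study procedures, "FDG PET scans for pancreatic lesions that are solid on CT scan or MRI". It sets no size limit. It rules out only minors and pregnant or nursing women.
- Section 2.1.2 has a single exclusion, unwillingness to undergo serial imaging.
- Section 3.3.2 lists the grounds for considering surgery: an enlarging lesion, symptoms, or a size threshold that depends on location.
- Section 3.2.2 sets a PET schedule for "Patients with solid lesions of the pancreas that are suspicious for PNETs that have not yet reached size criteria where surgery will be recommended". Patients enrolled under Amendment F are scanned at baseline and at one year. Those enrolled before it are scanned at their next imaging time point and again a year later.

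Section 8 does not say which PET supplies the uptake value. It does not limit the comparison to patients without an indication at the scan, and it does not adjust for lesion size.

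**The concern.** A predictor must be assessed in people who have not yet reached the outcome. The outcome here, requiring an operation, is driven by the 3.3.2 criteria, and some of these can be met on the day of the PET. A patient may enter with a lesion above the size threshold, or with symptoms, have the on-study PET, and later be counted as operated. If larger or symptomatic lesions take up more FDG, that patient raises the operated group's mean for reasons already visible on the same visit's CT or in the history.

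Prediction matters most for patients under observation, the 3.2.2 group. A difference confined to patients who already had an indication would say nothing about them, yet Section 8 would present it as predictive value. Section 8 also says that the two-yearly analyses may lead to revised surgical guidelines, so a mislabelled result could be acted on.

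**Working it through.** **Inputs from Section 8.** Planned: 52 patients with solid lesions, 26 operated and 26 not, 1 SD difference, t-test at 5%. Observed in April 2014: 129 with solid lesions, of whom 24 were operated on, so 129 − 24 = 105 were not.

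**Inputs not in the documents (assumed).** The number *m* of operated patients who already met a criterion at the PET, and the uptake shift in them. I vary *m* and set the shift to 1 SD, with no predictive value in everyone else.

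**Step 1: reproduce the plan's figure.** The noncentrality is d / √(1/n₁ + 1/n₂) = 1 / √(1/26 + 1/26) = 3.61 on 50 degrees of freedom. Two-sided power at 5% is 94.2%, which matches the stated 94%. The point does not rest on an arithmetic error.

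**Step 2: size of the spurious difference.** If *m* of n₁ operated patients are shifted by 1 SD, the expected difference in means is (m/n₁) × 1 SD. For 12 of 24 this is 0.5 SD; for 13 of 26 it is also 0.5 SD.

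**Step 3: how often the test is then significant.** Simulated with the two-sample t-test at 5%; the rates are subject to simulation error of a few tenths of a point.

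| Design | Already indicated (m) | Expected difference (SD) | Significant |
|---|---|---|---|
| 24 v 105 | 0 | 0 | 5% |
| 24 v 105 | 1 to 3 | 0.04 to 0.13 | about 5% to 8% |
| 24 v 105 | 6 (25%) | 0.25 | 19% |
| 24 v 105 | 12 (50%) | 0.50 | 57% |
| 24 v 105 | 18 (75%) | 0.75 | 90% |
| 26 v 26 | 6 (about 25%) | 0.23 | 11% |
| 26 v 26 | 13 (50%) | 0.50 | 38% |
| 26 v 26 | 20 (about 75%) | 0.77 | 75% |

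With a shift of 0.5 SD, the 24 v 105 rates at 25%, 50% and 75% fall to about 8%, 19% and 37%. Under these assumptions any excess over 5% is false, since uptake predicts nothing among patients still at risk.

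**Step 4: power after restriction.** Using the Step 1 formula for a 1 SD difference, with already-indicated operated patients removed:

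| Planned design | Power | 2014 counts | Power |
|---|---|---|---|
| 26 v 26 | 94% | 24 v 105 | 99% |
| 20 v 26 | 91% | 18 v 105 | 97% |
| 13 v 26 | 82% | 12 v 105 | 90% |
| 6 v 26 | 57% | 6 v 105 | 66% |

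These figures hold the non-operated group fixed. Non-operated patients who met a criterion at the PET would leave as well, so true power would be somewhat lower.

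**The case against.** The strongest reply is Section 3.2.2. Its PET schedule, which includes a baseline scan, sits under lesions "that have not yet reached size criteria where surgery will be recommended", so the PET cohort could be read as already limited to watched patients. Part of this stands: 3.1.3 and 3.2.2 can be read together in more than one way, and on the narrow reading the size criterion is largely dealt with. But 3.2.2 concerns follow-up and does not limit the on-study PET in 3.1.3. It also refers to size only, so a small lesion that is symptomatic or enlarging is still scanned. Enlargement needs serial imaging and cannot be shown by a first scan alone, but patients enrolled before Amendment F had their first PET during follow-up, when growth could already be known.

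The other objections stand and limit the point.

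- A reader might infer that the operated group is known to be mixed. No section reports that any operated patient already met a criterion at the PET.
- The phrase "will present or develop pancreatic tumors which require operation over follow-up" might seem to prove the mixing. It belongs to the growth-rate power calculation and can be read as tumours present at entry that become operable later.
- It is tempting to say that nothing is left to predict in already-indicated patients. That goes too far: Section 8 itself reports PET findings of non-neoplastic disease in which an operation could be avoided.
- The 129 are all patients with solid lesions, not all patients with a PET, so 24 v 105 overstates the numbers available.

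**Conclusion.** The concern holds as a gap in the definition of the analysis set. Groups "compared between patients who require operative intervention and those who do not" cannot support a claim of prediction unless patients with an existing indication at the scan are kept out, and no section keeps them out. Following the text as written could report current surgical status as prediction.

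The size is unknown. If only 1 to 3 of 24 operated patients were already indicated, the false-positive rate barely moves (about 5% to 8%). It becomes serious at shares of a quarter or more: 19% to 90% with the 2014 counts, 11% to 75% in the planned design. All of these rates assume a 1 SD shift in already-indicated patients and no predictive value in the rest. They illustrate sensitivity and do not estimate the bias in this study. The documents do not support the reading that the FDG result is already known to be spurious, and the stated 94% power is correct for the groups it describes.

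**What to change.** In Section 8:

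1. Name the index scan as the first on-protocol FDG PET.
2. Run the predictive comparison only in patients, operated or not, who met none of the 3.3.2 criteria, as the documents state them, at the visit of that PET.
3. Adjust for lesion size at the PET, because lesions just below a threshold remain in the set and size can drive both uptake and operation.
4. Report patients who already met a criterion separately, as a cross-sectional or detection result. The existing analysis of surgical patients in Section 8 (metastasis missed by CT, or non-neoplastic disease) is a natural place for it.
5. State how many operated patients remain and the power for that number, using the Step 4 figures as a guide.

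Counting how many of the 24 operated patients met a criterion at their index PET would show at once whether the issue is minor or serious.

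The cost is mainly wording and a lower stated power. Classification also needs some work. Symptoms are not among the items that Section 6.2.1 lists for the case report forms, so they must come from the medical record. Enlargement needs earlier scans, and 3.3.2 gives no numerical definition, so the basis for each classification should be recorded. If few operated patients remain, the size-adjusted estimate will be imprecise and should be reported with its confidence interval. No change to the surgery criteria is involved.

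### The FDOPA part of a primary objective is recorded as met, but the only FDOPA result reported is an 11% lesion-positivity rate, which does not address metastasis, progression or operation

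*Combined protocol and SAP*

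**What the plan says.** Section 1.1.1 (Primary Objectives) sets one objective for two tracers: "To determine if FDG and FDOPA PET scans can detect early tumor metastasis, and predict which patients will have tumor progression and require an operation", judged on uptake status. The note attached to it reads "Note: this objective has been met for FDOPA PET imaging" and refers the reader to Section 8.

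Section 8 (Statistical Considerations) describes the FDOPA evidence at February 1, 2011: "40 patients have been enrolled who have undergone all four imaging modalities". The result is "Only 11 of the 98 lesions (11%) were positive on 18F-DOPA as compared to CT scan". The conclusion is that "18F-DOPA is not likely to be useful for detecting pancreatic neuroendocrine tumors in patients with VHL", and the scan left the protocol at Amendment H. Section 1.2 (Background and Rationale) gives the same figure and conclusion directly after restating the metastasis and progression aim.

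The analysis that Section 8 plans against the operative outcome names FDG only: "The uptake levels of FDG on PET imaging will be compared between patients who require operative intervention and those who do not". The metastasis result in Section 8 (3 patients whose metastases CT did not show, at April 15, 2014) is also for FDG only.

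**The concern.** The objective asks about two outcomes: whether the scan finds early metastasis, and whether uptake separates patients who progress to operation from those who do not. The evidence cited for closing it is the share of lesions that took up the tracer, compared with CT. That describes how often FDOPA shows a pancreatic lesion. It does not link uptake to either outcome. A tracer taken up by few lesions may still mark the ones that behave badly, or it may not; a positivity rate cannot tell these apart.

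At stake is what the trial may claim on a primary objective. Someone reading the objectives would take FDOPA's value for metastasis and prognosis as settled, and Section 8 does not contain the result they are sent there to find.

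**Working it through.** **Inputs**
- FDOPA: 11 positive of 98 lesions; 40 patients with all four modalities by February 1, 2011 (Section 8).
- Operations: 24 of 129 solid-lesion patients at April 15, 2014; planning assumption 50%, that is 26 of 52 (Section 8).
- Planned FDG test: two-sample t-test, 5% level, 1 SD, 26 v 26, stated power 94% (Section 8). Two-sided is assumed.

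**Step 1. The plan's own figure.** 11/98 = 11.2%, which agrees with the stated 11%. The 95% Wilson interval is 6.4% to 19.0% if lesions are independent. There are 98/40 = 2.45 lesions per patient. With design effect 1 + (2.45 − 1) × ICC, the interval is 5.7% to 20.9% at ICC 0.3 and 4.7% to 24.6% at ICC 1 (the ICC is assumed). The arithmetic is not in dispute.

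**Step 2. The objective against what is reported.**

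| Element of the objective | FDG | FDOPA |
|---|---|---|
| Early metastasis | Result reported (3 patients missed by CT) | Nothing reported |
| Progression and operation, by uptake | Comparison planned, with power | Nothing planned or reported |
| Lesion positivity relative to CT (not in this objective) | – | 11/98 |

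The one filled FDOPA cell lies outside the objective.

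**Step 3. What 11.2% implies about operation.** With q the share positive and p the share operated on, sensitivity lies between max(0, (q + p − 1)/p) and min(1, q/p). These bounds assume that the operation rate can be carried over as shown.
- Lesion level, p = 24/129 = 18.6%: 0% to 0.112/0.186 = 60%.
- Lesion level, p = 50%: 0% to 0.112/0.50 = 22%.
- In both cases q < p, so the positive predictive value can be anything from 0% to 100%.
- Patient level: if the 11 positive lesions lay in 11 different patients, up to 11 of 40 would be positive. With 7 operated on, all 7 could be among them (100%); with 20 operated on, at most 11/20 = 55%.

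Low positivity therefore sets a ceiling in some scenarios, but it does not fix the association. No comparable bound can be formed for metastasis, because no FDOPA count is given.

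**Step 4. What a comparison in 40 patients could show.** Noncentrality = d/√(1/n₁ + 1/n₂), df = n₁ + n₂ − 2, two-sided 5%.
- Check on the plan: 26 v 26, d = 1 gives 1/√(2/26) = 3.61, df 50, power 94.2% (stated 94%).
- p = 18.6%: 40 × 24/129 = 7.4, so 7 v 33; noncentrality 1/√(1/7 + 1/33) = 2.40, df 38, power 64.9%. A power of 80% needs about 1.20 SD.
- p = 50%: 20 v 20; noncentrality 1/√(2/20) = 3.16, df 38, power 86.9%.

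**The case against.** The basis for closing the objective is disclosed. The note points to Section 8, which gives numerator, denominator, date and a conclusion limited to detecting tumours. Neither Section 8 nor Section 1.2 claims that prognosis was tested. An objective phrased as finding out whether something works can also be closed by a negative answer, and a rule based on uptake is less promising when few lesions take up the tracer. FDOPA has left the protocol, and no sample size, ongoing procedure or decision rule depends on the note.

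Much of this stands. It limits the harm and shows that the fault lies in the status note, since Section 8 describes Amendment H accurately. It does not rescue the note. Reading *met* as *closed after an unfavourable interim look* still leaves the two stated questions without a result, because 11 of 98 does not say whether the positive lesions were the ones that spread or went to operation.

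Three stronger readings are tempting, and the documents do not support them:
- That FDOPA's value for metastasis and progression was never evaluated. The documents show only that no such evaluation is reported in them.
- That 40 is the total number scanned with FDOPA. It counts patients who had all four modalities by February 1, 2011; others may have had FDOPA without the full set, or between that date and Amendment H.
- That the scans in hand are too few to be informative. This depends on an operation rate the documents do not give for these patients.

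**Conclusion.** The point holds as a mismatch between a primary objective and the evidence cited for closing it. The status *met* is not supported for FDOPA; *discontinued for low lesion detection* is. Nothing here argues that dropping the scan was wrong.

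That conclusion rests on the text alone. The power range of about 65% to 87% for a 1 SD difference rests on assumptions: 40 patients, and an operation rate of either 24/129, taken from all solid-lesion patients at a later date, or the planned 50%. It also ignores family clustering. With 100 − 11.2 = 88.8% of lesions negative, a comparison of means in SD units may describe uptake poorly. The range supports an exploratory label for any such analysis and no firmer statement.

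The consequence is for interpretation and reporting. Safety, conduct and sample size are untouched.

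**What to change.** 1. In Section 1.1.1, replace the note with: *FDOPA imaging was discontinued at Amendment H after an interim analysis showed low lesion detection; its relation to metastasis, progression and operation is not reported here.*
2. In Section 8, add an exploratory patient-level analysis of FDOPA uptake, both as positive/negative and as a level, against later operation and metastasis. Include all patients who had an FDOPA scan, which is at least the 40 with all four modalities by February 1, 2011. State how many were operated on, and report estimates with confidence intervals.
3. If such an analysis already exists, citing it in Section 8 would serve instead, and the note can then state what it found.

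The cost is a wording change and one analysis of scans already done and of follow-up the protocol already provides for. No new scans or patients are needed. The downside is that the objective is reported as unanswered for FDOPA unless that analysis answers it.
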